10.1.2.2. Laboratory data

Missing laboratory results (including immunological data) will not be replaced.

10.1.2.3. Solicited adverse events (*Amended 03-DEC-2020*)

- For a given subject and the analysis of solicited symptoms within 7 days post-vaccination, missing or non-evaluable measurements will not be replaced. Therefore, the analysis of the solicited symptoms based on the Exposed
- Set Cohort will include only vaccinated subjects for doses with documented safety data (i.e., symptom screen completed). More specifically the following rules will be used:
 - Subjects who documented the absence of a solicited symptom after vaccination will be considered not having that symptom after vaccination.
 - When a specific solicited adverse event is marked as having not occurred following a specific vaccination (i.e. SDTM CE.CEOCCUR=N for the specified post-vaccination period for the adverse event in question), all daily measurements will be imputed as Grade 0.
 - When a specific symptom is marked as having occurred following a specific vaccination (i.e. SDTM CE.CEOCCUR=Y for the specified post-vaccination period for the symptom in question), any missing daily recordings will be given imputed values to allow them to contribute to the ‘Any’ rows but not to specific grade rows of the symptom summary tables.
 - When a specific solicited adverse event is marked as having occurred following a specific vaccination (i.e. SDTM CE.CEOCCUR=Y for the specified post-vaccination period for the adverse event in question), any missing daily recordings will be given imputed values to allow them to contribute to the ‘Any’ rows, also counting this AE as “unknow” row of the solicited adverse event summary tables. Dose without symptom sheets documented will be excluded.

10.1.2.4. Unsolicited adverse events

Unsolicited adverse event summaries are including serious adverse events unless specified otherwise.

Missing severity, relationship with study vaccine, and outcome of unsolicited adverse events will not be replaced and will appear as ‘UNKNOWN’ in all statistical output.

10.1.3. Data derivation**10.1.3.1. Age at vaccination in years**

When age at vaccination is to be displayed in years, it will be calculated as the number of complete calendar years between the date of birth and the date of vaccination. For example:

DOB = 10SEP1983, Date of vaccination = 09SEP2018 -> Age = 34 years

DOB = 10SEP1983, Date of vaccination = 10SEP2018 -> Age = 35 years

10.1.3.2. Weight

Weight will be presented in kilograms. Weights reported in pounds will be converted as follows:

Weight in kilograms = Weight in pounds / 2.2

10.1.3.3. Height

Height will be presented in centimeters. Heights reported in feet and inches will be converted as follows:

Height in centimeters = Height in inches x 2.54

10.1.3.4. Body mass index (BMI)

BMI will be calculated as follows:

BMI = (Weight in kilograms) / (Height in meters)²

10.1.3.5. Temperature

Temperatures will be presented in degrees Celsius (°C). Temperatures reported in degrees Fahrenheit (°F) will be converted as follows:

Temperature (Celsius) = ((Temperature (Fahrenheit) - 32) x 5)/9

10.1.3.6. Numerical serology results

Numerical serology results will be derived from the content of IS.ISORRES in the SDTM dataset. For assays with a specific cut-off, the following derivation rules apply:

IS.ISORRES	Derived value
“NEG”, “-”, or “(-)”	cut-off/2
“POS”, “+”, or “(+)”	cut-off
“< value” and value is <= assay cut-off	cut-off/2
“< value” and value is > assay cut-off	value
“> value” and value is < assay cut-off	cut-off/2
“> value” and value is >= assay cut-off	value
“value” and value is < cut-off	cut-off/2
“value” and value is >= cut-off	value
All other cases	missing

10.1.3.7. Geometric mean titres (GMTs) and concentrations (GMCs)

Geometric Mean Titre (GMT) or Concentration (GMC) calculations are performed by taking the inverse logarithm of the mean of the log titre or concentration transformations. Antibody titres or concentrations below the cut-off of the assay will be given an arbitrary value of half the cut-off of the assay for the purpose of GMT/GMC calculation. The cut-off value is defined by the laboratory before the analysis and is described in the protocol.

10.1.3.8. Onset day

The onset day for an event (e.g. AE, medication, vaccination) is the number of days between the last study vaccination and the start date of the event. This is 1 for an event occurring on the same day as a vaccination (and reported as starting after vaccination).

10.1.3.9. Duration of events

The duration of an event with a start and end date will be the number of days between the start and end dates plus one day, i.e. an event that starts on 03MAR2018 and ends on 12MAR2018 has a duration of 10 days.

The duration of solicited events will be calculated as the sum of the individual days with the adverse event reported at grade 1 or higher during the solicited adverse event period.

10.1.3.10. Counting rules for combining solicited and unsolicited adverse events

For output combining solicited and unsolicited adverse events, all serious adverse events will be considered general events since the administration site flag is not included in the expedited adverse event CRF pages.

Multiple events with the same preferred term which start on the same day are counted as only one occurrence.

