### **12.5.7. Detecting and recording adverse events, serious adverse events and pregnancies**

A Paper Diary (pDiary) hereafter referred to as Subject Diary will be used in this study to capture solicited or unsolicited adverse events. The subject should be trained on how and when to complete each field of the Subject Diary.

The subjects will be instructed to contact the investigator immediately should the subject manifest any signs or symptoms they perceive as serious.

Subject Diary training should be directed at the individual(s) who will perform the measurements of adverse events and who will enter the information into the Subject Diary. This individual may not be the subject, but if a person other than the subject enters information into the Subject Diary, this person's identity must be documented in the Subject Diary. Any individual that makes entries into the Subject Diary must receive training on completion of the Subject Diary at the time of the visit when Subject Diary is dispensed. This training must be documented in the subject's source record.

At the vaccination visit, the diary card will be provided to the subject. The subject/ will be instructed to measure and record the body temperature (oral preferred), and any solicited local/general AEs (i.e. on the day of vaccination and during the next 6 days) or any unsolicited AEs (i.e. on the day of vaccination and during the next 30 days occurring after the 1st and 2nd vaccination. The subject will be instructed to return the completed diary card to the investigator at the next study visit.

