5.3. Analysis of safety and reactogenicity

5.3.1. Analysis of safety and reactogenicity planned in the protocol (Amended 03-DEC-2020)

The following safety analyses will be performed based on the Solicited Safety or Exposed Sets. The following safety analysis will be performed on the pooled data then the US and ex-US separately.

Endpoint	Statistical Analysis Methods
Primary	
(US + ex-US data to be pooled)
 
For each group with 1st dose vaccination of RSVPreF3 (two dose levels) when given alone or co-ad with dTpa; the following points will be analysed for 1st and 2nd dose vaccination.
 
The percentage of subjects with at least one local AE on left or right arm with at least one general AE and with any ("solicited or unsolicited") AE during the 7-day follow up period (the day of vaccination + 6 subsequent days) or 30 -day follow up period (the day of vaccination + 29 subsequent days) post 1st and 2nd vaccination period will be tabulated with exact 95% CI by study group. The same computations will be done for Grade 3 AEs, for any AEs considered related to vaccination, for Grade 3 AEs considered related to vaccination and for AEs resulting in medically attended visits.
 
The percentage of subjects reporting each individual solicited local AE (any grade, Grade 3 and those resulting in a medically attended visit) and solicited general AE (any grade, Grade 3, any related, Grade 3 related and those resulting in a medically attended visit) during the 7-day follow-up period (the day of vaccination + 6 subsequent days) will be tabulated based on maximum intensity for each group.
 
For fever, the number and percentage of subjects reporting fever by half degree (°C) cumulative increments during the 7-day follow-up period (the day of vaccination + 6 subsequent days) will be tabulated for each group. Similar tabulations will be performed for any fever with a causal relationship to vaccination, Grade 3 or above (> 39.0°C/102.2°F) causally related fever, and

Endpoint	Statistical Analysis Methods

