	
fever resulting in a medically attended visit. In addition, the prevalence of any and Grade 3 fever will be presented graphically over time after each vaccination.
 
The percentage of subjects with any unsolicited AEs during the 30-day follow-up period (the day of vaccination + 29 subsequent days) with its exact 95% CI will be tabulated by group and by Medical Dictionary for Regulatory Activities (MedDRA) system organ classes (SOC) and preferred term. Similar tabulation will be done for Grade 3 unsolicited AEs, for any causally related unsolicited AEs, for Grade 3 causally related unsolicited AEs and for unsolicited AEs resulting in a medically attended visit and leading to withdrawal from study. The verbatim term of unsolicited AEs will be reviewed by a physician and the signs and symptoms will be coded according to the MedDRA Dictionary for Adverse Reaction Terminology.
 
The percentage of subjects with at least one report of SAE classified by the MedDRA SOC and Preferred Terms and reported during the 30-day follow-up period (the day of vaccination + 29 subsequent days) will be tabulated with exact 95% CI. SAEs will also be described in detail.
 
The percentage of subjects using concomitant medication (any medication, any antipyretic and any antipyretic taken prophylactically, respectively) during the 7-day follow-up period and during the 30-day follow-up period will be summarized by each group and pooled.

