5.3.2. Additional considerations

5.3.2.1. Analysis of solicited events

The analysis of solicited events will be performed on Solicited Safety Set. The intensity of the following solicited events will be assessed as described:

Table 5 Intensity scales for solicited symptoms in adults

Adults/Child (≥6 years)		
Adverse Event	Intensity grade	Parameter
Pain at injection site	CC1 - This section contained Clinical Outcome Assessment data collection questionnaires or indices, which are protected by third party copyright laws and therefore have been excluded.	
Redness at injection site		
Swelling at injection site		
Temperature*		
Headache		
Fatigue		
Gastrointestinal symptoms (nausea, vomiting, diarrhoea and/or abdominal pain)		

CC1 - This section contained Clinical Outcome Assessment data collection questionnaires or indices, which are protected by third party copyright laws and therefore have been excluded.

The maximum intensity of solicited administration site redness/swelling will be scored at GSK Biological as follows:

CCI - This section contained Clinical Outcome Assessment data collection questionnaires or indices, which are protected by third party copyright laws and therefore have been excluded.

Duration in days of solicited local and general adverse events within 7 days after vaccination will be tabulated by study group and overall, and if needed by age group. The derivation rule of duration in days for solicited events is detailed in section [10.1.3.9](#).

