5.3.2.3. Combined Solicited and Unsolicited Adverse Events

The combined analysis of solicited and unsolicited events will be performed on Exposed Set. A summary of subjects with all combined solicited and unsolicited adverse events will be provided.

Solicited adverse events will be coded by MedDRA as per the following codes

Solicited symptom	Lower level term code	Corresponding Lower level term decode
Pain	Injection site pain	10022086
Redness	Injection site redness	10022098
Swelling	Injection site swelling	10053425
Fatigue	Fatigue	10016256
Fever	Fever	10016558
Headache	Headache	10019211
Gastrointestinal symptoms [†]	Gastrointestinal disorder	10017944

Please note – to check for AE term in CDISC during dry run

[†]Gastrointestinal symptoms include nausea, vomiting, diarrhoea and/or abdominal pain.

For [clintrial.gov](#) and [EudraCT](#) posting purposes, a summary of combined solicited and unsolicited adverse events will be produced by System Organ Class and preferred terms and according to occurrence of each event.

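### Classing every SAE as general in combined AE outputs can leave a serious injection-site reaction out of the local-AE percentage and add it to the general-AE percentage, in limited circumstances

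*SAP*

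**What the plan says.** The counting rule in the current SAP (Amendment 4), section 10.1.3.10, covers outputs that combine solicited and unsolicited events. It states that "all serious adverse events will be considered general events since the administration site flag is not included in the expedited adverse event CRF pages". The reason given is a limitation of the form.

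The output it reaches is in SAP 5.3.1, first as a primary analysis and again in the secondary analyses by formulation: "The percentage of subjects with at least one local AE on left or right arm with at least one general AE", together with any AE, over 7 days and over 30 days, after each dose. The same computations are repeated for Grade 3, related and medically attended events. Two further statements bring SAEs into these rows. SAP 5.3.2.3 says "The combined analysis of solicited and unsolicited events will be performed on Exposed Set", and SAP 10.1.2.4 says "Unsolicited adverse event summaries are including serious adverse events unless specified otherwise".

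Other parts of the plan capture or display the same events by separate routes:

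- Protocol 12.5.7 has the woman record on her diary "any solicited local/general AEs (i.e. on the day of vaccination and during the next 6 days"; the solicited local events are pain, redness and swelling (Protocol 12.5.3).
- SAP 5.3.2.1: "The analysis of solicited events will be performed on Solicited Safety Set".
- SAP 5.3.1 tabulates "The percentage of subjects with at least one report of SAE classified by the MedDRA SOC and Preferred Terms" and adds that "SAEs will also be described in detail".

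**The concern.** A serious injection-site event, such as an abscess or cellulitis that leads to admission, is a local reaction by nature. Under the rule it never enters the local row as an SAE; it enters the general row. Where nothing else puts the woman in the local row, the local percentage is understated. Where nothing else puts her in the general row, the general percentage is overstated.

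The error in the local row is in the reassuring direction, and reactogenicity of RSVPreF3 alone or with dTpa is a primary safety objective. The missing flag does not force this treatment: SAEs already carry MedDRA Preferred Terms, and SAP 5.3.2.3 itself uses injection-site terms to code the solicited local symptoms.

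**Working it through.** **The plan's own figures.** Protocol Table 18 uses exact two-sided 95% Clopper-Pearson limits. With no events, the upper limit is 1 − 0.025^(1/N): 7.11% at N = 50, 3.62% at N = 100 and 0.92% at N = 400, against the stated 7.1, 3.6 and 0.9. All 18 rows of the table reproduce to rounding.

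**When a percentage changes.** The rows count women with at least one event, so:

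- The local row loses a woman only if she has no other local AE that qualifies for that row and window.
- The general row gains her only if she has no other general AE that qualifies. Solicited fatigue, fever, headache and gastrointestinal symptoms all count here.
- The any-AE row does not change, because the event is counted under either label.

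Three situations meet the local condition most readily:

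1. Onset after Day 7. The diary solicits local events on the vaccination day plus 6 days, while the longer table covers 30 days.
2. A reaction in the first 7 days with no pain, redness or swelling on the diary.
3. The Grade 3 local row. A woman with Grade 1 diary pain and a Grade 3 serious injection-site event stays in the any-grade local row but is absent from the Grade 3 local row.

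**Size per affected woman.** The maximum shift is 100/N percentage points.

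| Group | N | Maximum shift | Upper limit, 0 women | Upper limit, 1 woman |
|---|---|---|---|---|
| One formulation | 50 | 2.0 points | 7.1% | 10.6% |
| Pooled formulations | 100 | 1.0 point | 3.6% | 5.4% |
| All RSVPreF3 groups | 400 | 0.25 point | 0.9% | 1.4% |

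The upper limit for one woman is the 97.5% quantile of a Beta(2, N − 1) distribution. In a well-filled row the change is hardly visible: 49/100 has limits 38.9 to 59.2, and 50/100 has limits 39.8 to 60.2.

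**How often.** The documents give no rate for serious injection-site reactions. As an assumption, take a rate p between 0.1% and 1%. The chance of at least one is 1 − (1 − p)^N: 9.5% to 63.4% at N = 100, and 33.0% to 98.2% at N = 400. The expected shift in the local percentage is p times the probability that the woman has no other qualifying local AE. If that probability lies between 5% and 100%, the shift runs from 0.1% × 0.05 = 0.005 point to 1% × 1 = 1.0 point.

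**The case against.** The strongest reply is that little is lost. Diary pain, redness or swelling in the first week will usually keep the woman in the any-grade local row. The individual solicited tables lie outside the rule. SAEs are tabulated by SOC and Preferred Term and described individually, and the unsolicited tables show them again. One related SAE triggers a hold on vaccination (Protocol 8.6, rule 1b). The rule is also disclosed, sits among the sponsor's standard conventions and applies alike to every group.

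All of that stands, and it rules out several stronger readings that a reader might infer:

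- That every serious local reaction drops out of the local percentage and inflates the general one. The rows count women, so the effect is conditional.
- That the most serious local reactions disappear from the safety results. They remain visible in the outputs just named.
- That the related local row could fall to 0/100. Protocol 12.5.7.2.2 deems all solicited local reactions related, so an empty row would need 100 women with no pain, redness or swelling at all.
- That the comparison with and without dTpa is biased. The rule is common to all groups, and nothing in the documents shows unequal occurrence.

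What the reply does not do is make the local row correct. Display elsewhere limits the importance of the misclassification without removing it.

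**Conclusion.** The concern holds in a limited form and is minor. A serious injection-site reaction can be missing from the local percentage, and can add to the general percentage, when the woman has no other qualifying event in that row and window. The cost is at most 1.0 point per woman at N = 100 and 2.0 points at N = 50. The clearest case is a sparse Grade 3 local row, where 0/100 (upper limit 3.6%) would be reported in place of 1/100 (5.4%). The any-AE percentage, the individual solicited tables and the SAE and unsolicited tables by SOC and Preferred Term are unaffected.

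This rests on two assumptions. The first is that unsolicited and serious events enter the local and general rows; SAP 5.3.1 does not say so row by row, but the 30-day window, SAP 10.1.2.4 and the existence of the counting rule all point that way. The second is that such events are few, and that the Grade 3 local row may be sparse; the documents give a rate for neither.

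**What to change.** In SAP 10.1.3.10, replace the blanket rule with one sentence: an SAE counts as local when its MedDRA Preferred Term is an injection-, vaccination- or administration-site term, and as general otherwise. Pair it with a short medical check of the SAE verbatim terms, done blinded to treatment for the first dose; the extension is open-label. The rule should not require attribution to an arm, because nothing in the documents shows that the expedited report records one, and the local/general split does not need it.

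The cost is one sentence and a small review effort. One limitation remains: if the reported term does not name the injection site, a cellulitis or abscess may still be classed as general. If the sponsor keeps the present convention, the minimum is a footnote on each combined table saying that SAEs are counted as general whatever their site.

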10.1.3.11. Counting rules for occurrences of solicited adverse events

When the occurrences of solicited adverse events are summarized, each event recorded as having occurred during a specific period will be counted as only one occurrence regardless of the number of days on which it occurs. Also, in the case of co-administered study vaccines, an injection site reaction recorded for a subject following multiple vaccines will be counted by as only one occurrence. However specific tables or figures could be conducted to report solicited local events by occurrence.

10.1.4. Display of decimals**10.1.4.1. Percentages**

Percentages and their corresponding confidence limits will be displayed with:

- no decimals when there are fewer than 50 subjects in each tabulated group
- one decimal when there are at least 50 subjects in at least one tabulated group
 - Exceptions will be made for percentages that are not 0% or 100% but appear as 0% or 100% due to rounding. For these specific cases the number of decimals will be increased until the displayed value is no longer 0% or 100%. Examples are given in the following table.

n/N	Displayed percentage
10/45	22%
1/45	2%
10/55	18.2%
1/55	1.8%
1/300	0.3%
1/3000	0.03%
1/30000	0.003%
299/300	99.7%
2999/3000	99.97%
29999/30000	99.997%

- The display of additional decimals for values close to 0% or 100% will be applied only to point estimates and not confidence limits, which can be rounded and displayed as 0% or 100%.
- Values of exactly 0% or 100% will be presented with no decimals regardless of the number of subjects per tabulated group.

10.1.4.2. Differences in percentages

Differences in percentages and their corresponding confidence limits will be displayed with one more decimal than the maximum number used to display the individual percentages, for example the difference between two percentages displayed with one decimal will be displayed with two decimals.

10.1.4.3. Demographic/baseline characteristics statistics

The mean, median, and standard deviation for continuous baseline characteristics (height, weight, body mass index (BMI), pre-vaccination body temperature) will be presented with one decimal.

The minimum and maximum values and quartile values (if required) will be presented with the same number of decimals as the observed values.

The maxima and minima of transformed height variables will be displayed with no decimals.

The maxima and minima of transformed weight variables will be displayed with no decimals with the exception of values are below 10kg where one decimal will be displayed.

The maximum and minima of transformed body temperatures will be displayed with one decimal.

10.1.4.4. Serological summary statistics

The number of decimals used when displaying geometric mean titers (GMT) or concentrations (GMC) and their confidence limits is shown in the following table:

GMT or GMC value	Number of decimals to display
<0.1	3
≥0.1 and <10	2
≥10 and <1000	1
≥1000	0

When multiple categories of GMT or GMC values are present in the same table, the number of decimals displayed should match that of the smallest category (i.e. the one with the higher number of decimals). For example, if GMT or GMC values of <0.1 appear in the same table as values of ≥0.1 and <10, 3 decimals should be displayed for both.

GMT or GMC ratios and their confidence limits will be displayed with 2 decimals regardless of the actual values.

